6.1.2. Treatment Period

During the 1.5-year study, each patient will receive up to 20 SC doses of ISIS 766720 with a planned monthly interval between each dose except for a booster dose at Day 15 (WK 3). All patients will have bi-weekly visits beginning at Day 1 (WK 1) through Day 113 (WK 17). After that visits occur monthly through Day 505 (WK 73) with an additional visit on Day 183 (WK 27) for primary endpoint assessments. Of the 24 required study visits, 14 selected study visits may be performed outside of the clinic by a Sponsor selected Home Health Care professional (See [Appendix A](#)). Home health visits are optional and would be arranged by study center staff if requested by the patient. In consultation with the Sponsor, a Home Health Care visit may be conducted for a study visit day that was intended to be an in-clinic visit. It is preferable that the entire visit is conducted, however the following assessments may be omitted: ECG, body weight, physical exam, ring size, and OGTT. If a visit cannot be performed in the clinic or by Home Health, patient contact (e.g., phone, text, email or video) is required by site personnel to assess any adverse events or changes in concomitant medications. Any assessments not completed at the Home Health Care visit should be attempted at the next clinic visit.

Safety, efficacy, PK and exploratory assessments will be performed per [Appendix A](#), [Appendix B](#), and [Appendix C](#) throughout the Treatment Period on ISIS 766720 administration days. At each visit, patients should arrive fasting at least 8 hours for safety and clinical laboratory evaluations; vital signs, blood pressure (BP) assessments, AEs and concomitant medication usage will be assessed during each visit.

A 2-hour OGTT and GH response procedure will be conducted pre-dose on Day 1 and pre-dose on Day 183 (WK 27) and Day 505 (WK 73). The pre-dose-Day 1 OGTT and GH response procedure may be conducted between Day -41 and pre-dose Day 1. To decrease the study burden on potential patients, it is suggested that this procedure is done after the patient has completed and qualified based on all other screening procedures. The OGTT and GH Response procedure can be conducted in the clinic or as arranged by a Home Health Care professional. The patient must fast 10-hours prior to OGTT and GH Response assessment.

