8.5. Safety Monitoring Rules

Please refer also to the 'Guidance for Investigator' section of the Investigator's Brochure.

For the purposes of safety monitoring Baseline is defined as:

- Monitoring Rules for Liver Chemistry Tests, Renal parameters, and Platelets – Unless otherwise specified, baseline is defined as the average of pre-dose values

In addition to the standard monitoring of clinical safety parameters, the following guidelines are provided for the monitoring of selected parameters chosen based on preclinical and clinical observations for ISIS 766720 as well as other ASOs.

Confirmation Guidance: At any time during the study (Treatment or Post-Treatment Periods), the initial clinical laboratory results meeting the safety monitoring criteria presented below **must be confirmed** by performing measurements (ideally in the same laboratory that performed the initial measurement) on new specimens. All new specimen collections should take place as soon as possible (ideally within 7 days of the initial collection). For stopping rules, if the initial laboratory result is observed during the Treatment Period, the results from the re-test **must be available** prior to administering the next dose of ISIS 766720.

Re-dosing Guidance: Patients with initial laboratory test values that reach a stopping rule must not be re-dosed until the re-test results are available. In general, patients who do not meet the

stopping rules based upon re-test may continue dosing. However, the Investigator and the Sponsor Medical Monitor (or appropriately qualified Designee) should confer as to whether additional close monitoring of the patient is appropriate. If any of the stopping criteria described in Section 8.6 are met, the patient will be permanently discontinued from further treatment with ISIS 766720, evaluated fully as outlined below and in consultation with the Sponsor Medical Monitor (or appropriately qualified Designee), and will be followed up in accordance with Section 8.8 of the Protocol.

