3.7.4. Laboratory Measurements

Bone biomarkers, pituitary axis, thyroid panel, inflammatory, lipid panel, chemistry, hematology, coagulation, cardiac biomarkers and urinalysis (result, change and percent change from Baseline) will be summarized at each post-baseline visit. Listing of laboratory assessments in Chemistry, Hematology and urinalysis will be provided. Local laboratory data will also be provided in the listings separately.

For Alanine Aminotransferase (ALT) and Aspartate Aminotransferase (AST), the number and percent of subjects falling in each of the following categories will be tabulated:

- ALT/AST $> 3 \times \text{ULN}$, confirmed
- ALT/AST $> 5 \times \text{ULN}$, confirmed

For Total Bilirubin (BILI), the number and percent of subjects falling in each of the following categories will be tabulated:

- BILI $> 1 \times \text{ULN}$, confirmed

A confirmed value is based on a consecutive lab value performed on a different day to, but within 7 days of, the initial value. If the repeated value is in the same or worse category, then the initial value is considered confirmed. If the consecutive value is in a better category, then the initial value is confirmed using the consecutive value category. If values that are not confirmed due to failure to retest or missing lab values, then the initial value is presumed confirmed.

If there are multiple results on the same day (no matter from the same lab vendor or different lab vendors), then the worst value will be utilized in the analysis.

The number and percentage of patients falling in each of the following categories (using available central and local laboratory assessments) based on post-baseline assessments will be provided:

- Confirmed Platelet count 100,000/mm³ to lower limit of normal (based on central lab)
- Confirmed Platelet count 75,000 to $< 100,000/\text{mm}^3$
- Confirmed Platelet count 50,000 to $< 75,000/\text{mm}^3$
- Confirmed Platelet count 25,000 to $< 50,000/\text{mm}^3$
- Confirmed Platelet count $< 25,000/\text{mm}^3$
- Confirmed $\geq 30\%$ Platelet count decrease from Baseline; further classifying by the lower limit of normal (Above or below)

Additional analysis to explore the possible thrombocytopenia incidence can also be found in AESI described in Section 3.7.1.

Subjects with more than one confirmed value will be counted exactly once under the worst confirmed category.

3.7.5. 12-Lead Electrocardiograms (ECG)

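### Three 'confirmed' platelet and bilirubin rows in SAP 3.7.4 will consist mostly of single values that the protocol never asks to be repeated

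*Combined protocol and SAP*

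**What the plan says.** SAP 3.7.4 defines confirmation by timing: "A confirmed value is based on a consecutive lab value performed on a different day to, but within 7 days of, the initial value". When a second value falls in the same or a worse category, the first is confirmed. When it falls in a better one, the better category is used. With no second value, the default applies: "If values that are not confirmed due to failure to retest or missing lab values, then the initial value is presumed confirmed". Each patient is then counted once, under the worst confirmed category.

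The rows built on this rule include total bilirubin above 1 × ULN, "Confirmed Platelet count 100,000/mm³ to lower limit of normal (based on central lab", and a platelet fall of at least 30%, split at the lower limit of normal.

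Protocol 8.5 requires retesting for a limited set of results, namely "the initial clinical laboratory results meeting the safety monitoring criteria presented below". On timing it says: "All new specimen collections should take place as soon as possible (ideally within 7 days of the initial collection". The schedule in protocol 6.1.2 is: "All patients will have bi-weekly visits beginning at Day 1 (WK 1) through Day 113 (WK 17". Visits are then monthly, with one added at Week 27.

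**The concern.** The presumption comes from protocol 8.6.1, the liver stopping rules. A retest is mandatory there, so a missing one is a real failure and presuming the worst is sensible. SAP 3.7.4 carries the same default into categories where no retest is requested. In those rows the exception becomes the usual route to 'confirmed', and because the worst confirmed category counts, a normal value at the next visit does not remove the flag.

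The wording also allows an opposite reading. If failure to retest means only a missed mandatory retest, the SAP does not say how these three rows are filled, and almost nothing in them could be confirmed. Two programmers could produce very different tables from the same data.

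Platelets and liver tests have their own monitoring and stopping rules in this protocol, and every randomised group receives active drug, so no concurrent background rate is available. With about 12 patients per planned group, one chance flag moves a row by 1/12 = 8.3 percentage points. (Safety tables are by maximum dose received, so actual denominators may differ.)

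**Working it through.** The plan gives no expected rate for these rows, so there is no figure of its own to reproduce beyond the visit count. Appendix A lists 24 treatment visits from Day 1 to Day 505, as protocol 6.1.2 states.

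**Step 1: which rows trigger a retest**

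| SAP 3.7.4 row | Retest ordered by the protocol? | Place |
|---|---|---|
| ALT/AST > 3 × or > 5 × ULN | Yes, then at least weekly once confirmed | 8.5, 8.5.1 |
| Platelets below 100,000/mm³ | Yes, weekly or more often | 8.5.2, Table 4 |
| Platelets 100,000/mm³ to LLN | No (above 100,000), scheduled visits only | Table 4 |
| Fall ≥ 30% to 100,000/mm³ or less | Yes, because of the count reached | 8.5.2, Table 4 |
| Fall ≥ 30% staying above 100,000/mm³ | No | Table 4 |
| Bilirubin > 1 × ULN | Not by itself; weekly only after confirmed ALT/AST elevation | 8.5.1 |

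A 30% fall reaches 100,000/mm³ when baseline is 100,000/0.70 = 142,857/mm³. From any higher baseline, a 30% fall triggers no retest.

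**Step 2: can a scheduled visit serve as the retest?** There are 23 treatment visits after Day 1 plus 3 post-treatment visits, so 26 post-baseline visits and 25 gaps between them. From the day numbers in Appendix A:

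- 9 gaps of 14 days (seven from Day 15 to Day 113, two around Day 183)
- 15 gaps of 28 days
- 1 gap of 43 days (Day 561 to Day 604)

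None is 7 days or less. Using the windows at opposite ends (±3 at Day 15, ±5 at Day 29, ±7 after that), the nine short gaps can shrink to between 14 − 7 − 7 = 0 and 14 − 3 − 5 = 6 days. The 28-day gaps cannot fall below 28 − 14 = 14 days, nor the 43-day gap below 43 − 14 = 29.

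**Step 3: size for the ≥ 30% fall**

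Inputs from the documents: one last pre-dose baseline value (SAP 3.2.1) and a threshold of ln 0.70 = −0.357. Assumptions: a count at each of the 26 visits, no drug effect, log-normal within-patient variation with CV 8% to 15%, and correlation ρ between successive values (baseline included) of 0, 0.5 or 0.7.

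Under independence, the chance at one visit is Φ(ln 0.70 / (CV × √2)). At CV 10% this is Φ(−0.357/0.1414) = Φ(−2.52) = 0.0058. The 26 visits share one baseline, so the chance of at least one flag was simulated (200,000 patients per cell). Each cell gives the percentage of patients with any such fall / with a fall also present at the next visit:

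| CV | ρ = 0 | ρ = 0.5 | ρ = 0.7 |
|---|---|---|---|
| 8% | 1.5 / 0.1 | 1.2 / 0.2 | 0.9 / 0.3 |
| 10% | 8 / 0.8 | 7 / 1.8 | 5 / 2 |
| 12% | 19 / 3 | 16 / 6 | 13 / 6 |
| 15% | 36 / 9 | 32 / 15 | 27 / 15 |

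Of 40 patients at CV 10% and ρ = 0, that is 40 × 0.08 = 3.2 against 40 × 0.008 = 0.3. The simulation counts every fall of 30% or more, including those that reach 100,000/mm³ and would be retested.

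**Step 4: the other two rows.** For an assumed independent chance p of an abnormal value per visit, the share flagged is 1 − (1 − p)^26. This gives 6.3% at p = 0.25% and 23.0% at p = 1%. If an independent retest must agree, p is replaced by p², giving 0.02% and 0.26%. Persistent abnormality within a patient would narrow this gap.

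**The case against.** The strongest reply is that the default is deliberate and conservative. It repeats protocol 8.6.1, errs toward over-counting, and feeds no efficacy, eligibility or stopping decision. Readers also have values and changes by visit and the laboratory listings, where a value that returns to normal at the next visit can be seen. All of this stands. It limits the consequence but does not justify the word 'confirmed' for an unrepeated value, or mixing true with presumed confirmations in one row.

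A reader might infer that values in these rows can never be confirmed. The documents do not support that. Windows can bring nine visit pairs within 7 days, bilirubin is repeated weekly after confirmed ALT/AST elevation, falls to 100,000/mm³ or below are followed weekly, and protocol 3.4 allows additional visits for abnormal results.

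A reader might also infer a fixed, large inflation factor. That depends on assumed CVs and on independence. With ρ = 0 the ratio is about 10 at CV 10% and 4 at CV 15%; with ρ of 0.5 to 0.7 it is about 2 to 6. For bilirubin, independence is doubtful: patients with values up to 1.5 × ULN are eligible, and those with Gilbert's syndrome may exceed it, so some will be persistently above ULN.

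Finally, confirming every category against the next result at any interval looks attractive, but it carries a risk. Where dosing may be paused or reduced (protocol 8.5.1.1 and Table 4), a late value taken after recovery would downgrade a genuine drug effect.

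**Conclusion.** The concern holds as a labelling and definition problem. On the literal rule, most isolated values in the three categories would be tabulated as confirmed without a repeat sample, including those that are normal at the next visit. The direction is over-counting, and no harm is hidden.

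The size is unknown from the documents. With no drug effect, CVs of 8% to 15% and serial correlation of 0 to 0.7, about 1% to 36% of patients show at least one fall of 30% or more, against about 0.1% to 15% when the next value must agree. These figures concern the platelet-fall row only and rest wholly on the assumed variability. The sampling argument does not depend on them.

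**What to change.** In SAP 3.7.4:

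- Report 'confirmed by retest' and 'single value, no retest within 7 days (presumed)' as separate rows. This also shows how often a mandated retest came later than 7 days, which the protocol's timing permits.
- For the three categories with no mandated retest, drop 'confirmed' from the single-value row and add a row for abnormality also present at the next available result.
- Keep the present rule for categories where the protocol mandates a retest.
- State that unscheduled bilirubin results count. SAP 3.2.1 admits unscheduled results to the abnormality summary and names AST, ALT, platelet and renal, but not bilirubin.

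The cost is SAP wording and minor programming, with no new samples. The small downside is a longer table and a less simple headline row. Keeping the single-value row means that a real but transient change stays visible.

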10.6.2. Safety Analysis

Treatment duration and amount of ISIS 766720 received will be summarized by treatment group and total. The TEAEs and serious TEAEs will be summarized for each treatment group and total using the Medical Dictionary for Regulatory Activities (MedDRATM) coding system, by system organ class, preferred term, relationship to ISIS 766720, and severity. Tables and/or narratives of treatment-emergent deaths, serious and significant AEs, including early withdrawals due to AEs, will also be provided.

Laboratory tests including chemistry panel, complete blood count with differential, coagulation panel, complement etc., will be summarized by study visits for each treatment group and total. These safety variables will also be presented as change and percent change from Baseline over time after ISIS 766720 administration, as appropriate. Vital sign, calculated BMI, and ECG measures will be summarized by treatment group and total. Concomitant medications will be coded using WHO Drug dictionary and summarized as well.

Echocardiograms will be assessed by an independent central reader. Change from baseline will be summarized for the following parameters, that may include left ventricular mass (LVM), LVM index (LVMi), LV ejection fraction, LV posterior wall thickness (LVPWT), peak velocity ratio (E/A), interventricular septum thickness (IVST) and isovolumic relaxation time (IVRT) whenever possible.

[figure not shown]

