For other endpoints, baseline is defined as the last non-missing value prior to the first administration of ISIS 766720.

Analytical visits:

In general, all post-baseline data will be summarized using the visit labels provided in the data. Multiple results with the same visit label will be averaged for the continuous variables, and the worst result will be used for the categorical variables. Results with visit labels as “Unscheduled” will not be included in the by-visit summary tables and figures except for determining baseline and the incidence of abnormality lab summary including AST, ALT, platelet and renal but will be presented in data listings.

For patients who had last dose prior to treatment termination, PD results greater than 3 weeks after the last dose (the date of last dose + 21 days) up to treatment termination will not be included in the by-visit summary tables and figures. Also, for patients who started other acromegaly medications in the post-treatment period, PD results after the start date of acromegaly medication will not be included in the by-visit summary tables and figures.

Other situations, such as required additional confirmation, will be described separately in the related endpoint analysis approach.

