Safety 12 lead ECG will be performed at the visits indicated in the protocol Schedule of Procedures.

The ECG data will include ventricular rate (VR), PR interval, QRS duration, QT, and corrected QT intervals, and overall interpretation.

For the continuous variables above, descriptive statistics (n, mean, standard error, standard deviation, median, 25th percentile, 75th percentile, minimum and maximum) of the results at each study visit, as well as the change and percent change from Baseline to each study visit, will be presented in summary tables; for the categorical responses to overall interpretation, the results at each visit will be summarized by counts and percentages. In addition, patients reported QT interval > 500 msec and QT interval increase more than 60 msec from Baseline will be summarized at each visit. All the ECG data collected will be listed.

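### Read literally, SAP 3.7.5 sets its only QT outlier categories on uncorrected QT, so the patient counts can shift with heart rate alone

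*Combined protocol and SAP*

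**What the plan says.** SAP 3.7.5 defines the ECG variables as follows: "The ECG data will include ventricular rate (VR), PR interval, QRS duration, QT, and corrected QT intervals, and overall interpretation". QT and corrected QT are thus two variables, and no correction formula is given.

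The continuous variables receive "descriptive statistics (n, mean, standard error, standard deviation, median, 25th percentile, 75th percentile, minimum and maximum) of the results at each study visit". Their absolute and percentage changes relative to Baseline are tabulated by visit too. The section then adds one categorical display: "patients reported QT interval > 500 msec and QT interval increase more than 60 msec from Baseline will be summarized at each visit". Neither threshold carries the word corrected. The section ends: "All the ECG data collected will be listed".

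Two other places bear on the point. SAP 3.2.1 sets the reference value for the change rule: "For other endpoints, baseline is defined as the last non-missing value prior to the first administration of ISIS 766720". It does not match on heart rate. Protocol 10.6.2 says only "Vital sign, calculated BMI, and ECG measures will be summarized by treatment group and total", so the visible protocol text supplies no corrected-QT category that could stand in for the one in the SAP.

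**The concern.** Uncorrected QT varies with heart rate. A fixed cut-off on it is too lenient when the heart is fast and too strict when it is slow. A change rule on it mixes any drug effect on repolarisation with whatever the heart rate did between Baseline and the visit. Because the section separates the two variables, a programmer following it word for word would build the outlier table on uncorrected QT.

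Safety and tolerability are a primary objective (Protocol 1.1.1; SAP 1.2.1), and ECGs are a listed safety endpoint (SAP 1.3.3). The treatment groups are doses of the same drug, so no untreated group is available to show how many flags heart rate alone would produce. With about 40 patients planned (SAP 3.1), one misclassified patient moves an overall percentage by 1/40 = 2.5 points.

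**Working it through.** The plan states no derived ECG figure to reproduce, so this checks the mechanism.

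**Inputs from the SAP:** thresholds of > 500 msec and of an increase > 60 msec from Baseline, both on QT interval (3.7.5).

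**Assumed, because the documents give none of them:** the correction formula, the heart rates and the starting QTc of 420 msec.

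**Formulas**, with RR = 60/HR:
- Fridericia: QTc = QT / RR^(1/3), so QT = QTc × RR^(1/3)
- Bazett: QTc = QT / RR^(1/2), so QT = QTc × RR^(1/2)

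**Rule 1, > 500 msec.** Example at 90 bpm: RR = 0.667, and 500 × 0.667^(1/3) = 437 msec. Each cell is Fridericia / Bazett, in msec.

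| HR (bpm) | Raw QT at which QTc = 500 | QTc when raw QT = 500 |
|---|---|---|
| 50 | 531 / 548 | 471 / 456 |
| 60 | 500 / 500 | 500 / 500 |
| 70 | 475 / 463 | 526 / 540 |
| 80 | 454 / 433 | 550 / 577 |
| 90 | 437 / 408 | 572 / 612 |
| 100 | 422 / 387 | 593 / 645 |

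Under Fridericia at 90 bpm, every raw QT above 437 and up to 500 msec (QTc above 500, up to 572) exceeds 500 once corrected but is not flagged. At 50 bpm, every raw QT above 500 and up to 531 msec (QTc above about 471, up to 500) is flagged although QTc does not exceed 500. A raw QT of exactly 500 is not flagged, because the rule is a strict inequality. The error runs both ways under either formula.

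**Rule 2, increase > 60 msec.**

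| HR change (bpm) | QTc change | Raw QT change, Fridericia / Bazett | Flagged on raw QT? |
|---|---|---|---|
| 60 to 90 | 420 to 485 (+65) | +4 / −24 | No; missed |
| 60 to 80 | 420 to 485 (+65) | +21 / 0 | No; missed |
| 80 to 50 | none (420) | +65 / +96 | Yes; false |
| 75 to 50 | none (420) | +56 / +84 | Bazett only |
| 70 to 50 | none (420) | +47 / +71 | Bazett only |
| 80 to 60 | none (420) | +38 / +56 | No |

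Fridericia, first row: 485 × (60/90)^(1/3) − 420 × (60/60)^(1/3) = 423.7 − 420.0 = 3.7. Third row: 420 × (60/50)^(1/3) − 420 × (60/80)^(1/3) = 446.3 − 381.6 = 64.7.

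A false flag on the change rule therefore needs a large fall in heart rate, and the size needed depends on the formula. A missed rise needs only a moderate increase in heart rate.

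**The case against.** The strongest reply is that corrected QT is not neglected. As one of the continuous ECG variables, it is summarised at each visit with its maximum, and its change from Baseline is tabulated too. A QTc above 500 msec at a scheduled visit would normally show as that visit's maximum. If the same statistics are given for change, which is the natural reading, a rise above 60 msec would show as the maximum change. The listings would identify the patient. This stands, and it limits the severity. It does not fill the gap completely: those tables do not count patients beyond a threshold, and under SAP 3.2.1 unscheduled results reach only the listings.

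A second reply is that QT interval may be loose shorthand for corrected QT. That is possible. The separate naming makes uncorrected QT the literal reading, but the fault may be an incomplete specification and not a deliberate choice. The repair is the same.

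Third, ECG is one of several safety endpoints, it is summarised descriptively, and none of the visible stopping rules in Protocol 8.6 uses QT. That also stands; the point concerns a table, not a decision rule.

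A reader might infer more: that true prolongation would go undetected, or that the counts are certain to be wrong. The documents support neither. The by-visit extremes and the listings remain, and no heart-rate or QT distribution is given from which to estimate how many patients would be misclassified.

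**Conclusion.** The point holds for the categorical table only. As written, both thresholds fall on uncorrected QT, and the resulting counts can be wrong in either direction. How far a patient can be misplaced is illustrated by the Fridericia figures: at 90 bpm QTc can reach 572 msec without tripping the > 500 rule, and at 50 bpm a QTc of about 471 can trip it. For the change rule, a 65 msec rise in QTc can go uncounted, while a false flag at constant QTc requires a heart-rate fall of roughly the 80-to-50 bpm kind. Bazett changes the figures but not the direction.

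These results rest on the assumed formulas, heart rates and starting QTc. They show what can happen to one patient, not how often it would happen in this trial. The information stays in the reported data, so this is a modest defect in a prespecified safety display that is worth correcting.

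**What to change.** In SAP 3.7.5, state that both categories (> 500 msec, and an increase of > 60 msec from Baseline) are evaluated on corrected QT, and name the correction formula. Use that same formula for the continuous summaries of corrected QT. Keep uncorrected QT as supportive information in the listings. Corrected QT is already among the collected variables, so the cost is one line of SAP wording and the matching change to the table specification, with no new data.
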